8.3 Reasons for Removal From Treatment, or Study

8.3.1 Reasons for Removal From Treatment

Reasons for removal from protocol-required IP(s) or procedural assessments include any of the following:

- subject request
- safety concern (eg, due to an adverse event, ineligibility determined, protocol deviation, non-compliance, protocol-specified criteria, pregnancy)
- death
- lost to follow-up
- decision by sponsor (other than subject request, safety concern, lost to follow-up)
- disease progression

Subjects who discontinue treatment will continue to be followed on the study.

8.3.2 Reasons for Removal From Study

Reasons for removal of a subject from the study are:

- decision by sponsor
- withdrawal of consent from study
- death
- lost to follow-up

9. SAFETY DATA COLLECTION, RECORDING, AND REPORTING

9.1 Definition of Safety Events

9.1.1 Disease Related Events

Disease Related Events are events (serious or non-serious) anticipated to occur in the study population due to the underlying disease, **eg, disease progression**. Such events do not meet the definition of an adverse event unless assessed to be more severe than expected for the subject's condition.

Disease Related Events that do not qualify as Adverse Events or Serious Adverse Events:

- An event which is part of the normal course of disease under study (eg, disease progression in oncology or hospitalization due to disease progression) is to be reported as a Disease Related Event.
- Death due to the disease under study is to be recorded on the Event CRF.

Approved

Disease Related Events that would qualify as an Adverse Event or Serious Adverse Event:

- An event based on the underlying disease that is worse than expected as assessed by the investigator for the subject's condition or if the investigator believes there is a causal relationship between the IP(s)/study treatment/protocol-required therapies and disease worsening, this must be reported as an Adverse Event or Serious Adverse Event.

Table 11. outlines the expected Disease-Related Events by System Organ Class.

Table 11. Disease-related Adverse Events by System Organ Class

SOC	Preferred Terms
Investigations	weight decreased
Blood and lymphatic system disorders	lymphadenopathy
General disorders and administration site conditions	disease progression fatigue
Skin and subcutaneous tissue disorders	night sweats
Other	hemorrhage ^c disease progression

SOC = system organ class.

9.1.2 Adverse Events

An adverse event is defined as any untoward medical occurrence in a clinical trial subject. The event does not necessarily have a causal relationship with study treatment. The investigator is responsible for ensuring that any adverse events observed by the investigator or reported by the subject are recorded in the subject's medical record.

The definition of adverse events includes worsening of a pre-existing medical condition. Worsening indicates that the pre-existing medical condition or underlying disease (eg, diabetes, migraine headaches, gout) has increased in severity, frequency, and/or duration more than would be expected, and/or has an association with a significantly worse outcome than expected. A pre-existing condition that has not worsened more than anticipated (ie, more than usual fluctuation of disease) during the study or involves an intervention such as elective cosmetic surgery or a medical procedure while on study, is not considered an adverse event.

If the severity of an adverse event changes from the date of onset to the date of resolution, record as a single event with the worst severity on the Event eCRF.

For situations when an adverse event or serious adverse event is due to lymphoma report all known signs and symptoms. Death due to disease progression in the absence of signs and symptoms should be reported as the primary tumor type (eg, R/R indolent NHL).

Note: The term “disease progression” should not be used to describe the disease related event or adverse event.

An adverse device effect is any adverse event related to the use of a medical device. Adverse device effects include adverse events resulting from insufficient or inadequate instructions for use, adverse events resulting from any malfunction of the device, or adverse events resulting from use error or from intentional misuse of the device.

The investigator’s clinical judgment is used to determine whether a subject is to be removed from treatment due to an adverse event. In the event a subject, or subject’s legally acceptable representative requests to withdraw from protocol-required therapies or the study due to an adverse event, refer to [Section 8.1](#) for additional instructions on the procedures recommended for safe withdrawal from protocol-required therapies or the study.

9.1.3 Serious Adverse Events

A serious adverse event is defined as an adverse event that meets at least 1 of the following serious criteria (unless it meets the definition of a Disease Related Event as defined in [Section 9.1.1](#)):

- fatal
- life threatening (places the subject at immediate risk of death)
- requires in-patient hospitalization or prolongation of existing hospitalization
- results in persistent or significant disability/incapacity
- congenital anomaly/birth defect
- other medically important serious event

A disease related event blood and lymphatic system disorders or investigations are to be reported as a serious adverse event if:

- the subject’s pre-existing condition becomes worse than what the investigator would consider typical for a patient with the same underlying condition, or
- if the investigator believes a causal relationship exists between the investigational medicinal product(s)/protocol-required therapies and the event,
- and the event meets at least 1 of the serious criteria.

Approved

An adverse event would meet the criterion of “requires hospitalization”, if the event necessitated an admission to a health care facility (eg, overnight stay).

If an investigator considers an event to be clinically important, but it does not meet any of the serious criteria, the event could be classified as a serious adverse event under the criterion of “other medically important serious event”. Examples of such events could include allergic bronchospasm, convulsions, blood dyscrasias, DILI (see [Appendix A](#) for drug-induced liver injury reporting criteria), or events that necessitate an emergency room visit, outpatient surgery, or urgent intervention.

If the criteria for grade 4 in the CTCAE grading scale for laboratory event differs from the regulatory criteria for serious adverse events, it is left to the investigator’s judgement **whether** to report these grade 4 abnormalities as serious adverse events.

9.2 Safety Event Reporting Procedures

9.2.1 Reporting Procedures for Disease Related Events

The investigator is responsible for ensuring that all Disease Related Events observed by the investigator or reported by the subject that occur after the first dose of investigational medicinal product(s)/study treatment/protocol-required therapies through the safety follow-up visit are recorded on the Event CRF as a Disease Related Event.

Disease Related Events assessed by the investigator to be more severe than expected and/or related to the investigational medicinal product(s)/study treatment/protocol-required therapies, and determined to be serious, must be recorded on the Event CRF as Serious Adverse Events.

Additionally, the investigator is required to report a fatal Disease Related Event on the Event CRF.

9.2.2 Adverse Events

9.2.2.1 Reporting Procedures for Adverse Events That Do Not Meet Serious Criteria

The investigator is responsible for ensuring that all adverse events observed by the investigator or reported by the subject that occur from the first dose of IP through the safety follow-up visit are reported using the Event CRF. Adverse events considered by the investigator to be possibly related to blinatumomab will be reported from the beginning of transplant conditioning during the long-term follow up until completion of a 2-year period after treatment.

Approved

The investigator must assign the following adverse event attributes:

- Adverse event diagnosis or syndrome(s), if known (if not known, signs or symptoms),
- Dates of onset and resolution (if resolved),
- Severity [and/or toxicity per protocol],
- Assessment of relatedness to blinatumomab or protocol required medication or medical device, and
- Action taken.

The adverse event grading scale used will be the CTCAE. The grading scale used in this study is described in [Appendix A](#).

The investigator must assess whether the adverse event is possibly related to blinatumomab. This relationship is indicated by a “yes” or “no” response to the question: Is there a reasonable possibility that the event may have been caused by the investigational medicinal product?

The investigator must assess whether the adverse event is possibly related to any study-mandated activity (eg, protocol-required therapies). This relationship is indicated by a “yes” or “no” response to the question: “Is there a reasonable possibility that the event may have been caused by a study activity (eg, protocol-required therapies), and/or procedure”?

The investigator is responsible for reviewing laboratory test results and determining whether an abnormal value in an individual study subject represents a change from the subject’s baseline values. All grade 3 and grade 4 laboratory values should be recorded as adverse events. In addition, if signs or symptoms are associated with a laboratory abnormality, the signs/symptoms and the laboratory abnormality should all be recorded as adverse events. The laboratory abnormality and any signs/symptoms should be graded according to their own CTCAE criteria.

The Investigator is expected to follow reported adverse events until stabilization or reversibility.

9.2.2.2 Reporting Procedures for Serious Adverse Events

The investigator is responsible for ensuring that all serious adverse events observed by the investigator or reported by the subject that occur after signing of the informed consent through safety follow-up are recorded in the subject’s medical record and are submitted to Amgen. In addition, blinatumomab related serious adverse events will be reported during the long term follow-up. All serious adverse events must be submitted to Amgen within 24 hours following the investigator’s knowledge of the event via the Event CRF.

If the electronic data capture (EDC) system is unavailable to the site staff to report the serious adverse event, the information is to be reported to Amgen via an electronic Serious Adverse Event Contingency Report Form within 24 hours of the investigator's knowledge of the event. See [Appendix B](#) for a sample of the Serious Adverse Event Worksheet /electronic Serious Adverse Event Contingency Report Form. For EDC studies where the first notification of a Serious Adverse Event is reported to Amgen via the eSerious Adverse Event Contingency Report Form, the data must be entered into the EDC system when the system is again available.

The investigator must assess whether the serious adverse event is possibly related to blinatumomab and/or other protocol-required therapies. This relationship is indicated by a "yes" or "no" response to the question: Is there a reasonable possibility that the event may have been caused by the IP?

The investigator is expected to follow reported serious adverse events until stabilization or reversibility.

New information relating to a previously reported serious adverse event must be submitted to Amgen. All new information for serious adverse events must be sent to Amgen within 24 hours following knowledge of the new information. If specifically requested, the investigator may need to provide additional follow-up information, such as discharge summaries, medical records, or extracts from the medical records.

Information provided about the serious adverse event must be consistent with that recorded on the Event CRF.

If a subject is permanently withdrawn from protocol-required therapies because of a serious adverse event, this information must be submitted to Amgen.

Amgen will report serious adverse events and/or suspected unexpected serious adverse reactions as required to regulatory authorities, investigators/institutions, and IRBs/IECs in compliance with all reporting requirements according to local regulations and GCP.

The investigator is to notify the appropriate IRB/IEC of serious adverse events occurring at the site and other adverse event reports received from Amgen, in accordance with local regulatory requirements and procedures.

9.2.2.3 Reporting Serious Adverse Events After the Protocol-required Reporting Period

There is no requirement to monitor study subjects for serious adverse events following the protocol-required reporting period or after end of study. However, these serious

adverse events can be reported to Amgen. In some countries (eg, European Union member states), investigators are required to report serious adverse events that they become aware of after end of study. If serious adverse events are reported, the investigator is to report them to Amgen within 24 hours following the investigator's knowledge of the event.

In addition to the attributes listed in [Section 9.2.2.1](#), the investigator must also complete the serious adverse event section of the Event eCRF.

Serious adverse events reported outside of the protocol-required reporting period will be captured within the safety database as clinical trial cases for the purposes of expedited reporting.

9.2.2.4 Serious Adverse Events That are not to be Reported by the Sponsors to Regulatory Agencies in an Expedited Manner

Events which are morbidities associated in general with lymphoma and lymphoma therapy do not require expedited reporting:

- Planned hospitalization

9.2.3 Reporting of Delayed Time to HSCT for Subjects With PR/PMR At Baseline

The investigator is responsible for reporting delays to HSCT in subject that meet the following criteria:

PR/PMR at baseline per Lugano classification and
Do not proceed to HSCT within 30 days of the first response assessment

These events will be recorded in the CRF and must be submitted to Amgen within 24 hours following the investigator's knowledge of the event. Refer to eCRF completion guidelines for specific reporting directions.

9.3 Pregnancy and Lactation Reporting

If a female subject becomes pregnant, or a male subject fathers a child, while the subject is taking blinatumomab, report the pregnancy to Amgen Global Patient Safety as specified below.

In addition to reporting any pregnancies occurring during the study, investigators should report pregnancies that occur 48 hours after the last dose of blinatumomab.

The pregnancy should be reported to Amgen Global Patient Safety within 24 hours of the investigator's knowledge of the event of a pregnancy. Report a pregnancy on the

Pregnancy Notification Worksheet ([Appendix C](#)). Amgen Global Patient Safety will follow-up with the investigator regarding additional information that may be requested.

If a female subject becomes pregnant during the study, the investigator should attempt to obtain information regarding the birth outcome and health of the infant. If a male subject's female partner becomes pregnant, the investigator should discuss obtaining information regarding the birth outcome and health of the infant from the pregnant partner.

If the outcome of the pregnancy meets a criterion for immediate classification as a Serious Adverse Event (eg, female subject experiences a spontaneous abortion, stillbirth, or neonatal death or there is a fetal or neonatal congenital anomaly) the investigator will report the event as a Serious Adverse Event.

If a female breastfeeds while taking protocol-required therapies report the lactation case to Amgen as specified below.

In addition to reporting a lactation case during the study, investigators should report lactation cases that occur 48 hours after the last dose of protocol-required therapies.

Any lactation case should be reported to Amgen Global Patient Safety within 24 hours of the investigator's knowledge of event. Report a lactation case on the Lactation Notification Worksheet ([Appendix C](#)). Amgen Global Patient Safety will follow-up with the investigator regarding additional information that may be requested.

10. STATISTICAL CONSIDERATIONS

10.1 Study Endpoints, Analysis Sets, and Covariates

10.1.1 Study Endpoints

10.1.1.1 Primary Endpoint

Phase 2 and Phase 3:

- CMR as determined by central radiographic assessment of PET/CT scans using the Lugano Classification

10.1.1.2 Secondary Endpoint(s)

Key Secondary Endpoints (phase 3 only):

- Overall Survival (OS): calculated as the time from the date of randomization until death due to any cause. Subjects who are alive at the date that triggers the analysis will be censored at the date last known to be alive. If the date last known to be alive is after the date that triggers the analysis, the subject will be censored at the analysis trigger date.

Other Secondary Endpoints:

Phase 2:

- Objective response rates (ORR **including** CMR and PMR)
- PFS: calculated as the time from start of blinatumomab until the date of diagnosis of progression of lymphoma, or date of death, whichever is earliest. Subjects who are alive and did not have progression will be censored at the last date of tumor assessment.
- DOR: calculated only for subjects who achieve an OR. The duration will be calculated from the date a response, CMR or PMR, is first achieved **per central review during the first 12 weeks after starting blinatumomab** until the earliest date of a disease assessment indicating a relapse event or death, whichever occurs first. Subjects who do not have a relapse event will be censored on their last disease assessment date. If the last disease assessment date is after the date that triggers the analysis, the subject will be censored at the analysis trigger date. A sensitivity analysis will censor subjects who receive a HSCT at the time of HSCT unless there is no assessment after the HSCT, in which case the last assessment prior to the HSCT will be used as the censoring time. **Disease assessment during LTFU will be reviewed by investigators only per central review agreement.**
- Successful mobilization rate (defined as CD34+ cell $2 \times 10^6/\text{kg}$)
- HSCT (both autologous and allogeneic) rates among subjects with post-blinatumomab CMR+PMR
- 100-day non-relapse mortality (NRM) after HSCT
- Blinatumomab steady state concentration and clearance
- Incidence and severity of treatment-emergent adverse events

Phase 3:

- OR (**including** CMR and PMR)
- PFS: calculated as the time from the date of randomization until the date of diagnosis of progression of lymphoma, or date of death, whichever is earliest. Subjects who are alive and did not have progression will be censored at the last date of tumor assessment.
- DOR
- Successful mobilization rate (defined as CD34+ cell $2 \times 10^6/\text{kg}$) following protocol assigned therapy
- HSCT (both autologous and allogeneic) rates among responding subjects (CMR or PMR)
- 100-day NRM after autologous HSCT rate
- Patient-reported clinical outcome assessments quality of life (QOLCOA) using the EQ-5D and FACT-Lymphoma tools
- Blinatumomab concentration steady state, clearance, and half life

Safety:

- Incidence and severity of treatment-emergent adverse events

10.1.1.3 Exploratory Endpoints

- Pharmacodynamics, including descriptive analysis of quantitative and qualitative features of lymphocyte populations and serum or plasma concentrations of cytokines
- Response rates and duration according to COO designation and c-myc and bcl-2 rearrangement and overexpression, R-IPI, Secondary IPI, NCCN IPI, as determined from pretreatment specimens
- Quantitative analysis of CF CT-DNA as determined by analysis of tumor-associated mutations in CF CT-DNA from plasma collected at various timepoints before, during, and after treatment

10.1.2 Analysis Sets

The primary analysis of efficacy from **the phase 2 part of the study will be performed on all subjects who received blinatumomab. The primary analysis of efficacy from the phase 3 part of the study will be performed on all randomized subjects analyzed according to their randomized treatment assignment (the Full Analysis Set [FAS]).**

Sensitivity analyses of efficacy will be performed on the Safety Analysis Set.

The primary analysis of safety will be performed on the Safety Analysis Set which will include all subjects who received protocol-specified therapy analyzed according to the treatment they received.

10.1.2.1 AutoHSCT Analysis Set

Includes all subjects who achieve a response and undergo autoHSCT **while in remission and without any other anti-cancer treatment.**

10.1.2.2 Full Analysis Set (FAS)

For the phase 2 part of the study, the FAS includes all subjects who are treated with blinatumomab.

For the phase 3 part of the study, the FAS Includes all subjects who are randomized. Analysis will be performed according to the randomized treatment, regardless of the treatment actually received.

10.1.2.3 Target Dose Analysis Set (TDAS)

All subjects of the FAS who completed at least 7 days of infusion on the highest intended dose level will constitute Target Dose Analysis set (TDAS). In addition, all subjects who discontinue the treatment due to progression of disease during the first cycle of treatment will be included. The primary efficacy endpoint will be analyzed using TDAS.

Approved

10.1.2.4 Responder Analysis Set

Includes all subjects who had CMR or PMR **during the first 12 weeks** after **initiation** of blinatumomab or IC chemotherapy (**for phase 3**).

10.1.2.5 Safety Analysis Set

Includes all subjects from both phases of the study who received protocol-specified therapy. Analysis will be performed according to the treatment received.

10.1.3 Covariates and Subgroups

The analysis to determine if blinatumomab is superior to IC arm with respect to the primary endpoint and key secondary endpoint **for phase 3** will be stratified by the stratification factors at randomization:

- Response to S1: PMR vs NMR/PMD
- Cytarabine administered in S1 (eg, R-DHAP and R-ESHAP vs R-ICE and R-GDP): yes vs no
- PMBCL and B-cell lymphoma, unclassifiable, with features intermediate between DLBCL and classical Hodgkin lymphoma vs all other histologies of aggressive B-cell lymphoma

10.1.4 Handling of Missing and Incomplete Data

Subjects missing post baseline disease assessments will be considered not to have achieved CMR.

Subjects not experiencing events that of interest for time-to-event endpoints (eg, deaths for OS) will be censored according to rules to be detailed in the statistical analysis plan.

10.2 Sample Size Considerations

10.2.1 Phase 2

The sample size for the phase 2 part of the study is determined by a 1-sample test of the rate of CMR **during the first 12 weeks** after **initiation** of blinatumomab. With the 1-sided type I error rate (α) set at 0.025, a null hypothesis response probability (π_0) of 15%, and an alternative response probability (π_1) of 40%, a sample size of 36 subjects will provide 90% power to reject the null hypothesis that the response probability is no more than 15%. Being able to make this determination will represent evidence of clinical activity and warrant advancement into the phase 3 part of the study.

10.2.2 Phase 3

The primary endpoint is CMR. A CMR rate of 22% in the IC arm vs. 40% in the blinatumomab arm is hypothesized. The odds ratio of CMR rate will be tested at the 1-sided significance level of 0.025. With these assumptions and a 1:1 randomization

ratio, a sample size of 296 subjects will provide 89% power. The sample size is adjusted for 3 interim futility analyses when 25%, 50%, and 75% of the subjects have had the opportunity to complete the tumor assessment and 1 interim efficacy analysis when 75% of the subjects have had the opportunity to complete the tumor assessment. The interim futility boundaries will use a Lan-DeMets beta-spending approach to an O'Brien-Fleming boundary and the interim efficacy boundaries will use a Lan-DeMets alpha-spending approach to an O'Brien-Fleming boundary. The details of these interim analyses are specified in the [Section 10.4.1](#).

Overall survival is a key secondary endpoint and the study is also powered for overall survival. If the null hypothesis for the primary endpoint is rejected, then OS will also be tested at a 1-sided significance level of 0.025. Assuming the true hazard ratio is 0.65 a final OS analysis after 236 death events will provide 90% power. With a median survival time of 4.4 months in the IC arm vs. 6.7 months in blinatumomab arm, accrual rates of 14.5 subjects per month, a 5% drop-out rate per year, and a targeted sample size of 296 randomized subjects, it is estimated that the 236th event will occur within 26 months of the start of randomization.

Sample size re-estimation will be allowed at an interim analysis (see [Section 10.4.1](#)).

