Among subjects achieving less than CR/CRu to second line therapy (n=177), the CR/CRu rate to third line therapy was 22%. The median OS of the entire cohort (ie, including those that achieved CR/CRu to second line therapy) was 4.4 months. For subjects achieving CR (n=55), PR (n=24), or SD/PD (n=87), OS at 1 year 77, 44, and 13%, respectively. Autologous HSCT was performed in 54, 58, and 22% of subjects with CR, PR, and SD/PD to S2 chemotherapy. Thirty subjects achieved CR and underwent HSCT; their 1 year survival was 82%. These results confirm that the majority of patients who do not respond to S1 chemotherapy are unlikely to respond to additional conventional chemotherapy. However, the survival experienced by responding subjects, particularly those in CMR, support the objective to introduce new agents in this setting.

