3. EXPERIMENTAL PLAN

3.1 Study Design

This is a phase 2/3 open label, multicenter trial testing blinatumomab monotherapy for the treatment of subjects with R/R aggressive B-NHL not achieving CMR after standard platinum-based chemotherapy regimens administered as S1. In the phase 3 part of the study, blinatumomab will be compared to IC chemotherapy. This study incorporates multiple interim analyses for futility, efficacy, and unblinded sample-size re-estimation, described further in [Section 10.4.1](#). The primary endpoint for both the phase 2 and 3 components of this trial is CMR rate, determined **during the first 12 weeks after initiation of blinatumomab or after initiation of IC chemotherapy for phase 3**.

Subjects with R/R aggressive B-NHL and considered by the investigator to be transplant eligible, but dependent upon the response to S2, will be enrolled after a minimum of 2 cycles of platinum-based S1 chemotherapy or if with PMD after 1 cycle of platinum-based S1 chemotherapy. In order to be eligible, subjects must undergo a restaging positron emission tomography/computed tomography (PET/CT) that is

interpreted centrally as demonstrating less than CMR. To optimize subject recruitment and retention, pre-screening discussions may be conducted with potential subjects prior to the initiation of S1 chemotherapy. However, enrollment may not occur until the PET/CT results are centrally reviewed and interpreted.

Subjects who experience clinical evidence of progression following at least 1 cycle of platinum-based S1 chemotherapy may be eligible but will require pre-S1 imaging and post-S1 PET/CT scan to confirm progression and to establish a new baseline for subsequent response assessment.

In the phase 2 component, enrolled subjects will receive blinatumomab monotherapy. In the phase 3 component, enrolled subjects will be randomized in a 1:1 ratio to blinatumomab or IC chemotherapy. Randomization will be stratified according to the following criteria:

Response to S1 chemotherapy (PMR vs no metabolic response [NMR]/ progressive metabolic disease [PMD])

Cytarabine administered in S1 (eg, R-DHAP and R-ESHAP vs R-ICE and R-GDP)

Primary Mediastinal B-Cell Lymphoma (PMBCL) and B-cell lymphoma, unclassifiable, with features intermediate between DLBCL and classical Hodgkin lymphoma vs all other histologies of aggressive B-cell lymphoma

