10.4.4 Final Analysis

The final analysis will test whether OS is superior in the group randomized to blinatumomab compared to the group randomized to IC. The final analysis will be triggered by the date when the 236th death in phase 3 subjects is reported in the clinical trial database, or the study duration reaches 12 months from the last subject randomized. The estimated time is 26 months to reach the OS event goal. Barring a sample-size increase, since the enrollment period is expected to last 21 months, the estimated maximum follow up time is 33 months.

In case that the phase 3 portion of the study is not initiated, the final analysis will occur when all subjects in phase 2 complete long term follow-up defined in [Section 7.2.7](#).

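### The month-26 estimate for the 236th death fits exponential survival, not the protocol's own 1-year survival data, so the 12-month cap would probably trigger the final OS analysis with fewer deaths

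*Protocol*

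**What the plan says.** Protocol Section 10.2.2 sets the OS design. On effect and events: "Assuming the true hazard ratio is 0.65 a final OS analysis after 236 death events will provide 90% power". On timing, it starts "With a median survival time of 4.4 months in the IC arm vs. 6.7 months in blinatumomab arm", adds "accrual rates of 14.5 subjects per month, a 5% drop-out rate per year, and a targeted sample size of 296 randomized subjects", and concludes that "it is estimated that the 236th event will occur within 26 months of the start of randomization". It names no survival distribution. Table 12 repeats the timeline, with about 153 deaths at month 18 and 236 at month 26.

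The control median comes from Section 2.1.4, which reports 4.4 months for the whole third-line cohort of a first-salvage trial. The same section reports 1-year survival by response: "For subjects achieving CR (n=55), PR (n=24), or SD/PD (n=87), OS at 1 year 77, 44, and 13%, respectively".

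The final analysis has a second trigger. Section 10.4.4 says it occurs at the 236th death "or the study duration reaches 12 months from the last subject randomized"; Sections 3.5.2, 7.2.7 and 7.2.8 agree. Section 10.5.3 describes the OS test only for the 236th death, and the final row of Table 15 is for 236 events. No event count, power or boundary is given for an analysis that the cap triggers.

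**The concern.** An exponential curve with a 4.4-month median leaves 15% of controls alive at 1 year. The planned 22% control complete metabolic response (CMR) rate, multiplied by the 77% 1-year survival quoted for complete responders, gives 16.9% alive from responders alone. Any survivors among the other 78% come on top of that. The source data therefore describe early deaths followed by a long tail, and with such a curve deaths arrive more slowly than planned.

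Slow events would only cost time if 236 deaths were the sole trigger. Because the calendar cap also triggers the final analysis, slow events mean fewer deaths at that analysis, lower OS power than the stated 90%, and a significance boundary that the protocol has not specified.

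**Working it through.** **Inputs.** Section 10.2.2: "then OS will also be tested at a 1-sided significance level of 0.025"; hazard ratio 0.65; medians 4.4 and 6.7 months; 14.5 subjects per month; 5% drop-out per year; 296 subjects. Section 3.1: "enrolled subjects will be randomized in a 1:1 ratio to blinatumomab or IC chemotherapy". Accrual lasts 296/14.5 = 20.4 months, so the cap falls at month 32.4 (about month 33 with the 21-month enrollment in Section 10.4.4).

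**1. Power at 236 deaths.** Schoenfeld: Φ(|ln 0.65| × √236 / 2 − 1.96) = Φ(3.309 − 1.96) = 91.1%. With the interim look and the Table 15 boundaries (0.005 and 0.023) it is 90.7%. The stated 90% reproduces.

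**2. Timeline.** Expected deaths, with uniform accrual, exponential survival and exponential drop-out, are 156 at month 18 (stated about 153), 238 at month 26 (stated 236) and 264 at the cap. The timeline reproduces, and under it the cap does not bind. Of the curves tried, only the exponential does this. With 20% alive at 1 year, at most 224 deaths are expected by month 26.

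**3. Control 1-year survival.**
- Exponential with a 4.4-month median: 0.5^(12/4.4) = 15.1%.
- The 166 subjects with a reported response: (55 × 0.77 + 24 × 0.44 + 87 × 0.13)/166 = 64.22/166 = 38.7%.
- All 203 subjects, counting the other 37 as dead within a year: 64.22/203 = 31.6%.
- CR share set to the planned 22%: 0.22 × 0.77 + 0.78 × (24/111 × 0.44 + 87/111 × 0.13) = 32.3%.
- Both adjustments: 32.3% × 0.82 = 26.5%.

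**4. Deaths and power with a matching curve.** The control curve has constant hazard ln 2/4.4 to month 4.4, then constant hazard to the chosen 1-year value. The blinatumomab curve is the control curve raised to the power 0.65. Accrual and drop-out are as in step 2. Each range runs from no deaths after month 12 to the month 4.4-12 hazard continuing unchanged.

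| Control 1-year survival | Deaths, month 18 | Deaths, month 26 | Deaths, cap | Power at cap |
|---|---|---|---|---|
| 15.1% (exponential) | 156 | 238 | 264 | cap does not bind |
| 26.5% | 131-136 | 184-206 | 191-233 | 85-91% |
| 32.3% (central) | 123-127 | 169-188 | 174-212 | 81-88% |
| 38.7% | 114-117 | 153-167 | 157-186 | 77-84% |

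Power is the Schoenfeld formula at the expected deaths; allowing for the interim look lowers it by less than one percentage point. It falls below 90% at 226 deaths. A Weibull curve through 50% at 4.4 months and 32.3% at 12 months gives 184 deaths at month 26, 202 at the cap and 86.5% power, inside the central range.

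**5. When 236 deaths would arrive.** In the mildest case (26.5%, hazard continuing) this is about month 33.5. In the central case it is about month 42 if the hazard continues, about month 59 on the Weibull curve, and never if no deaths occur after month 12.

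**The case against.** The strongest reply is that nothing is miscalculated: every stated figure reproduces, and under the stated assumptions the cap is harmless. That stands. A reader might infer that the 90% power rests on exponential survival, or that it is wrong. The documents do not support this. The power statement is tied to 236 deaths and a hazard ratio of 0.65 and needs only proportional hazards. Curve shape affects when deaths occur and, through the cap, how many there are.

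A reader might also infer that the OS test will certainly be underpowered. That is not shown either. The mildest case gives 233 deaths and about 91% power.

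The source populations are also mixed. The 4.4-month median covers all 203 subjects, whereas the response-group figures total 166, which matches the 82% who were treated. Of those treated, 13% were in complete response after first salvage, whom this trial excludes. The time origin of the 1-year figures is not given. The 38.7% is therefore the upper end rather than a best estimate, and the two adjustments correct for the mix only partly. Even so, with both of them 26.5% is well above 15.1%.

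Curve choice is open to challenge. A Weibull curve through 38.7% has shape 0.31 and implies about 24% of controls dead within a week, which is implausible for these subjects. The ranges above therefore come from the piecewise curves, whose hazard to month 4.4 is the plan's own.

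The sample size increase of up to 50% in Section 10.4.1 could add deaths, but promising-zone results trigger it, not an event shortfall. Finally, OS is a key secondary endpoint tested only after CMR succeeds, starting phase 3 is a later decision (Section 3.5.2), and the SAP covers only the single-arm part. These points limit the importance of the issue but do not answer it.

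**Conclusion.** The concern holds for the timeline and its consequence, not for the power formula. The month-26 estimate conflicts with the 1-year survival quoted from the source of the control median. With curves that respect both, the expected count is 153-206 deaths at month 26 and 157-233 at the cap, below 236 in every case examined, although the mildest comes close. The final OS analysis would then probably be triggered by the cap. Power there is about 81-88% in the central case, a loss of 2-9 percentage points against the stated 90%, and 77-91% over the full range.

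This rests on proportional hazards at 0.65, the planned accrual and drop-out, and an assumed tail after month 12, for which the documents give no data. It also keeps the hazard ratio rather than the 6.7-month blinatumomab median, because the power statement is built on the hazard ratio. It bears on the trial only if phase 3 is run.

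**What to change.** In Protocol Section 10.2.2, state the survival distribution used. Recompute expected deaths at month 26 and at the cap with a control curve that matches both the 4.4-month median and the 1-year survival in Section 2.1.4, and show the assumed range for survival after month 12. Correct the month-26 estimate there and in Table 12 and Section 10.4.4. In Sections 10.4.4 and 10.5.3 and Table 15, state the OS power for a final analysis triggered by the cap, and state that its alpha-spending boundary will be computed from the deaths actually observed.

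This costs wording and a short recalculation. The downside is a less favourable stated timeline and power. Removing the cap is optional and not part of this fix: in the central case the 236th death would come at about month 42 or later, against a cap at about month 32-33.
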